2.4.2 Monitoring by Study Monitoring Committee (SMC)

An IMPAACT SMC will review the study. The frequency of SMC review will be determined by the accrual rate or specific AEs and is planned to occur at least annually. Reports for the annual review may be minimal if accrual rate is slow. The SMC may also be convened upon request of the protocol team.

During the annual review, the Core Team may request the SMC focus on specific safety aspects, such as ECG data review. Note that SMC reports may be minimal if these types of events are rare and/or if accrual has been slow.

In addition, an *ad hoc* SMC review or consultation will occur, as noted below, by the following:

- (1) In the event of a **fatal or life-threatening AE, as assessed by the site in consultation with the Core Team**, the Core Team will review the AE and assess its relationship to study drug.
 - If the site investigator and/or the Core Team assesses the AE as **possibly, probably, or definitely related to study drug**, accrual will be paused. The Core Team will discuss how the study should proceed and consult with the SMC.
 - If the site investigator and the Core Team assess the AE as **probably not or not related to study drug**, accrual will continue. The SMC will be informed of the AE along with the Core Team's assessment and decision-making.
- (2) Within each cohort, and under the current dosing regimen: For N=6, if at least two participants within a cohort experience a grade 3 or non-life-threatening grade 4 AE at least probably related to study drug as assessed by the Core Team; OR for N=12, if at least three participants within a cohort experience a grade 3 or non-life-threatening grade 4 AE at least probably related to study drug as assessed by the Core Team; OR for N=18, if at least four participants within a cohort experience a grade 3 or non-life-threatening grade 4 AE at least probably related to study drug as assessed by the Core Team, then the SMC will be notified of this.
- (3) If > 25% of participants within a given cohort experience a QTcF > 500 ms then the SMC will be notified of this.
- (4) In the event of any unresolvable disagreement within the Core Team on an issue that would impact decision-making or if the Core Team encounters any other event or trend of concern, an SMC review of the relevant data will be convened.

3 Outcome Measures

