1.2 Version History

The original version of the SAP was updated (V 1.1) to account for Letter of Amendment (LoA) #2, dated 28 February 2019, and LoA #3, dated 17 October 2019, for Protocol Version 1.0, dated 3 March 2016, and included updates to the Bedaquiline (BDQ) dosing regimen for all cohorts, as was determined by population PK modeling performed based on PK data for the first 12 evaluable participants in Cohort 1 (consistent with protocol Sections 3.2 and 10.2.3). In addition, this version also accounts for Clarification Memorandum (CM) #6, dated 1 April 2020, which provided guidance to sites for conducting study visits and procedures during the COVID-19 pandemic and recommended prioritization for conduct of clinically and scientifically important evaluations.

The next version 1.2 accounted for LoA # 4 dated 27 June 2022, which incorporated contents of protocol CM #6 that provided operational flexibility for conducting study visits and procedures when needed and to prioritize the conduct of clinically and scientifically important evaluations when possible. Consistent with the instructions provided in CM #6, implementation of this LoA is expected to be time-limited in relation to the COVID-19 pandemic.

Version 2 reflected updates based on Protocol Version 2.0, dated 21 September 2022, with CM #1, dated 29 March 2023.

This current version just notes the version change based on LoA #1 dated 2 May 2023 to Protocol Version 2.0/

2 Study Overview

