2.3 Overview of Sample Size Considerations

At least 54 and up to 84 participants will be enrolled in the study across three age cohorts, as follows:

- Cohort 1: ≥ 6 to < 18 years of age at enrollment
- Cohort 2: ≥ 2 to < 6 years of age at enrollment
- Cohort 3: ≥ 0 to < 2 years of age at enrollment

Up to 24 participants in Cohort 1, up to 30 participants in Cohort 2, and up to 30 participants in Cohort 3 will be enrolled to achieve at least 18 evaluable participants in each cohort. In Cohort 1, up to 12 participants will be enrolled in each of the two weight bands (15 to < 30 kg and ≥ 30 kg) to achieve approximately nine evaluable participants in each weight band.

Participants are considered PK-evaluable if they have completed the intensive PK sampling collection and have at least one sample with measurable BDQ and M2 concentrations. Participants will be assessed by the Core Team for evaluability once PK data from the intensive PK visit are available. Regardless of evaluability, the safety population for this study will include all participants who receive at least one dose of study drug.

Non-evaluable participants will be replaced unless the maximum accrual of 24 participants in Cohort 1 and 30 participants in Cohorts 2 and 3 is already achieved. It is possible for the maximum number of participants to be enrolled in a cohort and not achieve the required 18 evaluable participants; however, the sample size per cohort was determined to accommodate loss of participant data due to non-evaluability or loss to follow-up.

The sample size is primarily based on PK considerations. Clinical trial simulations were performed to ensure a sample size able to provide precise enough estimates of apparent clearance as specified by the US Food and Drug Administration (FDA) criteria for pediatric trials. Since BDQ exposure over long-term administration primarily is determined by the apparent clearance, the first point implies that the primary objective of the study (to determine BDQ doses for children that achieve similar weekly exposure as adults taking BDQ at the current standard recommended dose) can be fulfilled.

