2.4 Overview of Monitoring

2.4.1 Interim Monitoring

There will be two interim analyses of PK and safety data for each age cohort, for a particular dosing scheme, during the dose-finding phase. The first will occur when six participants under the current BDQ dosing scheme have completed their intensive PK sampling at the Week 1 or Week 2 visit (see Sections 6.3 and 6.4 of the protocol). If the first six participants have acceptable PK and safety profiles, as evaluated by the Core Team, a second interim analysis will occur when 12 participants under the current BDQ dosing scheme have completed their intensive PK sampling.

During each interim analysis, the safety data will be considered “unacceptable” if the following conditions are met, as assessed by the Core Team (*only among evaluable participants in the cohort under evaluation for the current dosing scheme*):

- 1) Any fatal or life-threatening adverse event (AE) assessed by the Core Team to be at least possibly related to study drug occurs.
- 2) For N=6: At least two participants experience a grade 3 or non-life-threatening grade 4 AE assessed by the Core Team as at least probably related to study drug.
- 3) For N=12: At least three participants experience a grade 3 or non-life-threatening grade 4 AE assessed by the Core Team to be at least probably related to study drug.
- 4) For N=18: At least four participants experience a grade 3 or non-life-threatening grade 4 AE assessed by the Core Team to be at least probably related to study drug.

The safety data will be reviewed concurrently with PK data and whether PK criteria are met or not.

NOTE: At the time of finalization of this document, all planned interim PK and safety analyses for all cohorts have been completed.

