3.1 Primary Outcome Measures (evaluated through week 24)

- Termination from treatment due to a drug-related AE
- AEs of \geq grade 3 severity
- AEs of \geq grade 3 severity assessed by the Core Team to be at least possibly related to the study drug
- Absolute QTcF interval \geq 500msec
- Unstable dysrhythmias requiring hospitalization and treatment
- Death (grade 5 AE)

3.2 Secondary Outcome Measures (evaluated through Week 96 / 72 weeks post BDQ discontinuation)

- AEs of \geq grade 3 severity

- AEs of \geq grade 3 severity assessed by the Core Team to be at least possibly related to the study drug
- Absolute QTcF interval \geq 500msec
- Unstable dysrhythmias requiring hospitalization and treatment
- Death (grade 5 AE)

NOTE: For the outcome measures 3.1 and 3.2 above, for creatinine events under protocol Version 1.0, serum creatinine grading for the study analyses will be based on the absolute value only as per the DAIDS AE Grading Table (Corrected Version 2.1, dated July 2017) and not on percentage change from the participant's baseline value. This is consistent with creatinine grading requirements in protocol Version 2.0.

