 - Summary of reportable protocol deviations per IMPAACT Network Manual of Procedures
3. Baseline characteristics
4. Summary table for key characteristics, including sex, age, race, ethnicity, weight, height, Growth Z-scores, TB diagnostic category, TB disease type, and HIV status, TB Medication History, and key laboratory parameters
5. Study status
 - Number on treatment
 - Number off study prematurely, by reason and arm
 - Consort diagram (for final analyses only)
6. Safety Summary, in aggregate and by cohort
 - The proportions and listing of participants experiencing AE triggers as defined in protocol Section 9.5.2.
 - The listings and proportions of participants meeting the following primary endpoints:
 - Termination from treatment due to a drug-related AE
 - AEs of grade ≥ 3 severity
 - AEs of grade ≥ 3 severity assessed by the Core Team to be at least possibly related to the study drug
 - Absolute QTc interval ≥ 500 msec
 - Unstable dysrhythmias requiring hospitalization and treatment
 - Death (grade 5 AE)
 - Listing of QTcF over time (including mean QTcF across all participants per study week)
7. TB Treatment Outcome (included in SMC report if data are available)

8. HIV-1 RNA and CD4 summary statistics, and ARV experience for participants living with HIV
9. Data Completeness Report (no tables, summary will be provided in text)

6 Associated Documents

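### The QTcF trigger for SMC notification is not limited to the current BDQ regimen, so in Cohort 1, read literally, it can be diluted by children treated on an earlier regimen

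*SAP*

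**What the plan says.** SAP Section 2.4.2 lists four routes to an ad hoc SMC review or consultation. Trigger (3) is the only one that names QTcF: "If > 25% of participants within a given cohort experience a QTcF > 500 ms then the SMC will be notified of this". It gives no regimen limit and does not define the denominator further.

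The two neighbouring rules do carry a limit. Trigger (2) opens "Within each cohort, and under the current dosing regimen" and counts related grade 3 or non-life-threatening grade 4 events (2 of 6, 3 of 12, 4 of 18). The interim safety rule in Section 2.4.1 applies "only among evaluable participants in the cohort under evaluation for the current dosing scheme".

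Section 1.2 says the BDQ regimen was updated for all cohorts, "based on PK data for the first 12 evaluable participants in Cohort 1". Section 2.3 sets the maximum enrolment: "Up to 24 participants in Cohort 1, up to 30 participants in Cohort 2, and up to 30 participants in Cohort 3", with a target of 18 evaluable in each.

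Section 4.1 says the proportions meeting each SMC trigger will be reported descriptively. Section 5, item 6, presents the safety summary overall and by cohort, with no split by regimen.

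The QT event is worded in three ways: strictly above 500 ms in trigger (3); "Absolute QTcF interval \geq 500msec" in Section 3.1; and "Absolute QTc interval ≥ 500 msec" in Section 5, item 6, where the correction is not named.

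**The concern.** A QTcF trigger is useful if it reflects the regimen that children are now receiving. If the denominator also holds children from an earlier regimen, and few of them had an event, the proportion for the current regimen is pulled down and the rule becomes less sensitive after each regimen change. The plan treats regimen as essential elsewhere: the primary safety set is restricted to the final implemented dose, and trigger (2) is counted within regimen. QTcF of 500 ms or more is itself a primary outcome, yet its trigger lacks that limit. The same diluted proportion could also appear in the report of trigger endpoints.

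**Working it through.** **Nothing to reproduce.** The 25% figure is a design choice, and the documents give no derivation or operating characteristics for it.

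**Inputs from the SAP.** Threshold above 25% of the cohort (2.4.2); Cohort 1 target 18 evaluable, maximum 24 (2.3); regimen change after 12 evaluable Cohort 1 children (1.2).

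**Assumptions.** The documents do not give the number of children on each regimen, say whether any switched, or give QTcF event rates. I take 0, 6, 12 or 18 children on the earlier regimen, an earlier rate of 0% or 10%, and a current rate of 30% or 50%.

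**Step 1: count needed to fire.** Smallest count above 25% of N = floor(0.25 × N) + 1. This gives 2 of 6, 4 of 12, 5 of 18 and 7 of 24.

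**Step 2: largest silent count on the current regimen, with no earlier events.** This is the smaller of floor(0.25 × cohort total) and the number on the current regimen.

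| Cohort 1 total | Earlier | Current | Largest silent count | Share of current | Fires within regimen at |
|---|---|---|---|---|---|
| 18 | 0 | 18 | 4 | 22% | 5 |
| 18 | 6 | 12 | 4 | 33% | 4 |
| 18 | 12 | 6 | 4 | 67% | 2 |
| 24 | 0 | 24 | 6 | 25% | 7 |
| 24 | 6 | 18 | 6 | 33% | 5 |
| 24 | 12 | 12 | 6 | 50% | 4 |
| 24 | 18 | 6 | 6 | 100% | 2 |

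In the 12 + 12 case, 6/24 = 25.0% does not exceed 25%, so 7 of the 12 current children (58%) are needed. If the earlier 12 also had a 25% rate (3 events), at most 3 of 12 current children would go unflagged, because 3 + 3 = 6. The dilution then disappears.

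**Step 3: chance that trigger (3) fires.** For X ~ Binomial(n, p), P(X ≥ r) = Σ C(n,k) p^k (1 − p)^(n−k), summed from k = r to n.

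For 12 + 12 at a true current rate of 50%:
- Pooled, no earlier events: P(X ≥ 7) = 1586/4096 = 0.39.
- Pooled, earlier rate 10%: Σ over j of P(j earlier events) × P(X ≥ 7 − j) = 0.63.
- Within the current regimen: P(X ≥ 4) = 3797/4096 = 0.93.

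Other splits at a true current rate of 50%:

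| Earlier + current | Pooled, earlier 0% | Pooled, earlier 10% | Current regimen only |
|---|---|---|---|
| 12 + 6 | 0.11 | 0.41 | 0.89 |
| 6 + 12 | 0.81 | 0.87 | 0.93 |

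For 12 + 12 at a true current rate of 30% and no earlier events, the chance is 0.04 pooled against 0.51 within regimen.

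**Step 4: the cut-off wording.** Above 500 and at or above 500 differ only for a reading of exactly 500 ms. This adds nothing to the figures above.

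**The case against.** A reader might infer that half the children on the current regimen could exceed 500 ms without the SMC hearing of it. The documents do not support that; only trigger (3) would be silent. Under trigger (1) the SMC is consulted on or informed of every fatal or life-threatening event. Trigger (2) would fire at 3 of 12 on the current regimen if the QT events were graded 3 or 4 and judged at least probably related. Trigger (4) convenes a review for any event or trend of concern, and the SMC reviews the study at least annually, possibly with an ECG focus. This stands. Still, trigger (2) depends on grading and attribution, trigger (4) on the Core Team's judgement and the ECG focus on its request, so none guarantees notification on QTcF alone.

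A reader might also infer that the plan sets out to pool regimens. It does not say so; pooling is the literal reading of an unqualified cohort count. Section 5 refers to protocol Section 9.5.2 for the triggers. The protocol document supplied is Clarification Memorandum #1, which does not reproduce that section, so a scope set there cannot be checked here. Even so, the SAP wording differs from the rule directly above it.

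The 50% figure is a worst case for one split. Mixed regimens are evidenced only for Cohort 1, and children who switched might belong in the current-regimen count. All planned interim analyses are complete, so little effect on dose selection remains. The primary safety set and the by-dose secondary analyses will show QTcF on the implemented dose undiluted. These points limit the size of the problem; they do not supply the missing scope.

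Finally, a count on the current regimen alone would drop earlier-regimen events from the rule. That is a fair criticism of a simple substitution, and the fix allows for it.

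**Conclusion.** The point holds in limited form. Trigger (3) lacks the current-regimen limit that trigger (2) and the interim rule carry, and read literally it can be diluted in Cohort 1. With 12 earlier children, no events among them, 12 current children and no switching, it stays silent at 6 of 12 instead of firing at 4 of 12. Its chance of firing at a true 50% rate is then 0.39 (0.63 with a 10% earlier rate), against 0.93 within regimen. Across the other mixed Cohort 1 splits examined, with no earlier events, the unflagged share runs from 33% to 100%; with a single regimen it is at most 25%. The practical stake is ongoing SMC oversight and the reported trigger proportion, not dose finding.

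A reader might link the differing cut-offs to the dilution. They do not cause it. They are a separate, minor inconsistency: a notification threshold need not equal an outcome definition, and the unnamed correction in Section 5 appears in a list of the primary endpoints, where Section 3.1 names QTcF.

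**What to change.** In Section 2.4.2, keep the 25% figure and apply trigger (3) within each cohort under the current dosing regimen as well as cohort-wide, so that events on an earlier regimen still count. State the denominator and how children who changed regimen are counted. In the final report, show the trigger proportion by regimen beside the cohort figure. Align protocol Section 9.5.2 if its wording is the same.

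Separately, reconcile the QT event across Sections 2.4.2, 3.1 and 5: one correction formula, and either one inequality or a stated reason for two. No position is taken on which cut-off is right.

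The cost is a wording change and one extra split of a planned table. The downside is an occasional extra notification when few children are on a regimen: with three children, one event is 1/3 = 33% and fires the rule. Trigger (3) calls only for notification and does not itself pause accrual.

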3.1 Primary Outcome Measures (evaluated through week 24)

- Termination from treatment due to a drug-related AE
- AEs of \geq grade 3 severity
- AEs of \geq grade 3 severity assessed by the Core Team to be at least possibly related to the study drug
- Absolute QTcF interval \geq 500msec
- Unstable dysrhythmias requiring hospitalization and treatment
- Death (grade 5 AE)

3.2 Secondary Outcome Measures (evaluated through Week 96 / 72 weeks post BDQ discontinuation)

- AEs of \geq grade 3 severity

- AEs of \geq grade 3 severity assessed by the Core Team to be at least possibly related to the study drug
- Absolute QTcF interval \geq 500msec
- Unstable dysrhythmias requiring hospitalization and treatment
- Death (grade 5 AE)

NOTE: For the outcome measures 3.1 and 3.2 above, for creatinine events under protocol Version 1.0, serum creatinine grading for the study analyses will be based on the absolute value only as per the DAIDS AE Grading Table (Corrected Version 2.1, dated July 2017) and not on percentage change from the participant's baseline value. This is consistent with creatinine grading requirements in protocol Version 2.0.

3.3 Secondary TB treatment outcomes

- TB treatment outcome (see Protocol Section **Error! Reference source not found.**) at Week 96/End of Study or Early Study D/C visit, classified as bacteriological cure with no TB recurrence, probable cure with no TB recurrence, TB recurrence, death, treatment failure, or lost to follow-up.
- TB treatment outcome (see Protocol Section **Error! Reference source not found.**) at end of RR-TB treatment, classified as bacteriological cure, probable cure, death, treatment failure, or lost to follow-up.

4 Statistical Principles

4.1 General Considerations

The primary safety analyses will focus on the 24-week time period during BDQ treatment and will include only participants whose total exposure to BDQ was at the final implemented dose for their cohort for the protocol-specified period of BDQ administration. Participants who have been removed from treatment, or who have had their doses reduced as part of cohort management due to toxicities, will be included and treated as safety failures in the primary safety analysis (note that such participants may have to be excluded from any secondary analyses which require complete follow-up at the optimal dose). Participants whose doses have been adjusted on the basis of PK results will be excluded from the primary safety analyses, regardless if the participant initiated BDQ at the final implemented dose, and sensitivity analyses performed in an attempt to determine whether the exclusion of these participants creates a selection bias which impacts upon any results. These primary analyses will be performed after the last participant of the last cohort has completed the study drug regimen over the 24-week dosing period.

Each participant's safety data will be summarized as: (1) the most severe grade of AEs, and (2) the most severe grade of AEs assessed to be at least possibly related to study treatment. Frequency distributions of these safety outcomes will be presented in aggregate and will be broken down by age cohort. Listings of all \geq grade 3 events will be provided.

The proportions of participants experiencing \geq grade 3 AEs will be presented in aggregate and broken down by age cohort, with these proportions bounded by exact 95% CIs. If sample size allows, frequencies and proportions will be presented by weight band; similarly, by HIV status, broken down by age cohort and/or in aggregate. Similar analyses will present the proportions of participants exhibiting \geq grade 3 events which have been assessed to be at least possibly related to study drug, again bounded by exact 95% CIs. Tabulations will also be presented to summarize all AEs, as well as all AEs which have resulted in treatment discontinuation. Summary statistics of QT values at each time point performed will also be presented. Additionally, listings of participants who experience unstable dysrhythmias requiring hospitalization and treatment will be presented.

In addition, if possible, a primary evaluation of safety across the 24 weeks of study treatment will be performed on the data from participants who initiated the final recommended BDQ dose for a given cohort and remained on that dose for the 24-week period or have left the study or had a dose modification due to safety failure prior to 24 weeks of exposure (in which case the participant will be analyzed as a failure). Note that such an analysis may not be possible, since the PK modeling procedure which will determine the final recommended dose will not guarantee that any participant, or an adequate number of participants, be on that dose. However, secondary safety analyses will include all safety data collected from first participant exposure to the end of the study, with results broken down by dose. This will include data representing the final implemented dose for each cohort, as well as data gathered during the dose finding stage, which may represent exposure to doses which have failed.

Given that the modest sample sizes within cohorts will provide limited power for statistical tests of differences across age cohorts, only very large apparent effects would be statistically significant. Interpretation of differences across cohorts will depend upon whether these differences are great enough to be considered to be clinically significant. If no such differences are observed, then the clearest interpretation of the findings will come from the aggregated data, where analyses will have the greatest statistical precision. However, if results vary across cohorts to a clinically important extent, interpretation of results should consider the age differences and potential treatment differences represented by this stratification factor.

The proportions of participants meeting each of the endpoints which would trigger an *ad hoc* SMC review will be presented descriptively. Details concerning the analyses will be included in a separate analysis plan.

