The primary safety analyses will focus on the 24-week time period during BDQ treatment and will include only participants whose total exposure to BDQ ~~has been~~ was at the final ~~BDQ dose~~ ~~recommended~~ **implemented dose** for their cohort for the protocol-specified period of BDQ administration. Participants who have been removed from treatment, or who have had their doses reduced as part of cohort management due to toxicities, will be included and treated as safety failures in the primary safety analysis (note that such participants may have to be excluded from any

secondary analyses which require complete follow-up at the optimal dose). Participants whose doses have been adjusted on the basis of PK results will be excluded from these primary analyses, regardless if the participant initiated BDQ at the final ~~recommended~~ **implemented** dose, and sensitivity analyses performed in an attempt to determine whether the exclusion of these participants creates a selection bias which impacts upon any results. These primary analyses will be performed after the last participant of the last cohort has completed the study drug regimen over the 24-week dosing period.

2. *Section 9.6.1, Primary Safety Analyses, fourth paragraph:*

In addition, if possible, a primary evaluation of safety across the 24 weeks of study treatment will be performed on the data from participants who have been started at the final recommended dose for a given cohort and have remained on that dose for the 24-week period or have left the study or had a dose modification due to safety failure prior to 24 weeks of exposure (in which case the participant will be analyzed as a failure). Note that such an analysis may not be possible, since the PK modeling procedure which will determine the final recommended dose will not guarantee that an adequate number of participants be on that dose. However, secondary safety analyses will include all safety data collected from first participant exposure to the end of the study, with results broken down by dose. This will include data representing the final **implemented** dose for each cohort, as well as data gathered during the dose finding stage, which may represent exposure to doses which have failed.

3. *Section 9.6.2.1, Safety, first paragraph:*

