4.3 Safety Analysis Sets

The primary analysis set consists of all participants whose total exposure to the study drug BDQ was at the final implemented dose for their cohort for the protocol-specified period of BDQ administration. Participants who discontinued study drug due to toxicities will be considered a safety failure for this primary safety outcome measure* and will be considered an intercurrent event for the other primary safety outcome measures. Those who have had their doses adjusted as part of cohort management due to toxicities will be treated as safety failures* in the primary safety analysis. Participants who have been removed from study treatment for any reason (other than toxicity*) will be considered as having experienced an intercurrent event and will be included in the primary analysis dataset. These participants will be analyzed with the approach that those who experienced a primary safety outcome measure while on study drug will be considered as safety failure for that outcome measure. Those who were off study before the Week 24 visit due to reasons other than death will be included and will not be considered as a safety failure unless this was experienced before they were off study and while on study drug. The following sensitivity analyses will also be performed for participants who were off study before the Week 24 visit:

- The participant will be treated as safety failure (worst case)
- The participant will be excluded from the safety analysis set

Supplementary safety analysis dataset: All participants who were exposed to the study drug BDQ, including those who did not receive the final implemented dose evaluated in the study, as well as those whose dosing was amended based on PK considerations. The analysis approach will follow the same approach as that for the primary analysis set.

*Note that this refers to the relevant primary safety outcome (for example if the toxicity is “AEs of at least Grade 3 severity assessed by the Core Team to be at least possibly

related to study drug" then the participant will be considered a safety failure for this particular outcome measure only)

5 Report Contents

Detailed descriptions of the content of each of the following sections are given in the AIP.

1. Accrual
 - Screening (will be summarized in text only)
 - Number screened
 - Screening failure reasons
 - Enrollment
 - Number enrolled
2. Protocol deviations

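### SAP 4.1, Clarification Memorandum item 1 and the opening of SAP 4.3 tie the primary safety set to the full BDQ dosing period, while the rest of 4.3 includes participants who stop early for non-toxicity reasons

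*SAP*

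**What the plan says.** **SAP 4.1 (General Considerations), first paragraph.** The primary safety analyses "will include only participants whose total exposure to BDQ was at the final implemented dose for their cohort for the protocol-specified period" of BDQ administration. One group is then brought back in: "Participants who have been removed from treatment, or who have had their doses reduced as part of cohort management due to toxicities". They are to count as safety failures. Participants whose dose was changed because of PK results are excluded, with a sensitivity analysis for selection bias.

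**Clarification Memorandum 1, item 1 (protocol Section 9.6.1, first paragraph).** The rule is the same. Removed or dose-reduced participants "will be included and treated as safety failures in the primary safety analysis", with no statement of which outcome they fail.

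**SAP 4.3 (Safety Analysis Sets).** The first sentence repeats the condition: exposure at the "final implemented dose for their cohort for the protocol-specified period of BDQ administration". The section then sets out:
- Non-toxicity removal: "Participants who have been removed from study treatment for any reason (other than toxicity*) will be considered as having experienced an intercurrent event", and these participants belong to the primary dataset.
- How they are counted: "those who experienced a primary safety outcome measure while on study drug will be considered as safety failure for that outcome measure".
- Off study: "Those who were off study before the Week 24 visit due to reasons other than death will be included and will not be considered" failures, unless the event came earlier and on drug.
- Two sensitivity analyses, for off-study participants only: "The participant will be treated as safety failure (worst case") and exclusion from the set.
- A footnote limiting failure to the outcome that the toxicity concerns.

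**The concern.** Take a participant who receives the cohort's final implemented dose, stops BDQ at, say, Week 10 for a reason unrelated to toxicity, and has had no event. Under the full-period condition this person does not belong to the primary set. Under the detailed text of 4.3 the same person is a member and a non-failure. A programmer working from 4.1 and one working from 4.3 could produce different denominators. If a leaver had an event on drug, the numerators would differ too.

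The full-period condition is also the poorer rule on its merits. It selects participants on completion, which is known only after treatment starts. It would also drop a grade 3 or higher event that happened on the drug and at the dose under study, if that participant later left for another reason.

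These proportions are primary outcomes, reported in aggregate and by cohort with exact 95% CIs, and SAP 1.1 says they will be posted publicly. Leaving the set defined in two ways allows the choice to be made after the data are seen.

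**Working it through.** **Step 1. Set the texts side by side for one case: BDQ stopped early, not for toxicity.**

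| Text | In the primary set? | Failure? |
|---|---|---|
| 4.1 and memo item 1 | No, on the natural reading: the dosing period was not completed and the re-inclusion does not name this group | Not applicable |
| 4.3, first sentence | No, for the same reason | Not applicable |
| 4.3, later text | Yes | Only for an outcome that occurred on study drug |

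Non-failure is explicit in 4.3 for event-free participants who are off study. It is implied for those off BDQ but still followed.

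**Step 2. Can the texts be reconciled?** They can if the condition limits the dose level and not the duration. Two points weigh against that. The words about the dosing period would do no work, and participants removed for toxicity would need no express re-inclusion. The separate evaluation at the final recommended dose (SAP 4.1, continued) also uses a completion rule: 24 weeks on the dose unless a safety failure intervenes.

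**Step 3. Size.** The plan gives no event or leaver counts for this analysis, so there is no figure of its own to reproduce. Every count below is assumed. The 54 is borrowed from the PK-evaluable target (3 × 18) and is not a safety denominator; 84 is the enrolment ceiling (24 + 30 + 30).

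Let N be the number in the set under 4.3, E those with a grade 3 or higher AE on drug, L the non-toxicity leavers, and k the leavers with such an event.
- 4.3 rule: E/N
- Exclusion: (E − k)/(N − L)

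The two agree when k/L = E/N. Exclusion gives the higher figure when leavers had proportionally fewer events, and the lower figure when they had more. Intervals are Clopper-Pearson 95%.

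N = 54, E = 8. The 4.3 rule gives 8/54 = 14.8% (6.6 to 27.1). Exclusion gives:

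| L | k = 0 | k = 2 |
|---|---|---|
| 3 | 8/51 = 15.7% (7.0 to 28.6) | 6/51 = 11.8% (4.4 to 23.9) |
| 6 | 8/48 = 16.7% (7.5 to 30.2) | 6/48 = 12.5% (4.7 to 25.2) |
| 9 | 8/45 = 17.8% (8.0 to 32.1) | 6/45 = 13.3% (5.1 to 26.8) |

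With L = 6 and k = 1, exclusion gives 7/48 = 14.6% (6.1 to 27.8), almost the 4.3 figure, because the break-even is 6 × 8/54 = 0.89 leaver events.

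Other settings:
- N = 84, E = 12, L = 9: the 4.3 rule gives 12/84 = 14.3% (7.6 to 23.6). Exclusion gives 12/75 = 16.0% (8.6 to 26.3) with k = 0, or 10/75 = 13.3% (6.6 to 23.2) with k = 2.
- One cohort, N = 18, E = 3, L = 2: the 4.3 rule gives 3/18 = 16.7% (3.6 to 41.4). Exclusion gives 3/16 = 18.8% (4.0 to 45.6) with k = 0, or 2/16 = 12.5% (1.6 to 38.3) with k = 1.
- No events, N = 54, L = 6: both rules give 0%, with upper limits of 6.6% (0/54) and 7.4% (0/48).

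With no non-toxicity leavers, the two rules give the same proportion.

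**The case against.** **Section 4.3 already answers the question.** It is the section on analysis sets, 4.1 is general, and 4.3 places the restrictive sentence directly before the inclusion of leavers, so its authors evidently saw no conflict. Neither 4.1 nor the memo names non-toxicity leavers; their exclusion is an inference. Much of this stands: 4.3 is probably what is meant. But the tension also lies inside 4.3, no supplied text gives it precedence, and the supplied protocol text carries only the 4.1 wording.

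**The sensitivity analyses expose the issue.** For off-study participants they do, since both alternatives are shown. They do not reach participants who are off BDQ and still followed.

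**Early non-toxicity loss may be rare.** That is possible. SAP 2.3 mentions loss to follow-up, but in the context of reaching the PK-evaluable number, so it is weak evidence about loss up to Week 24.

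**A stronger reading.** A reader might infer from 4.1 that every participant removed from treatment, for whatever reason, is a primary safety failure, by attaching the toxicity phrase to dose reduction alone. That would move the proportions far more. The documents do not support reporting such a figure: 4.1 defines the proportion as participants who experience a grade 3 or higher AE, SAP Section 5 reports participants meeting each listed endpoint, and the 4.3 footnote is outcome-specific. An event-free leaver does not meet that definition.

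**Conclusion.** The inconsistency is real and should be corrected, but its consequence is modest. The full-period condition in 4.1, memo item 1 and the opening of 4.3 does not fit the later text of 4.3. In addition, 4.1 and the memo lack the footnote's limit of failure to the relevant outcome.

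On the assumed aggregate counts (54 in the set, 8 events, 3 to 9 leavers, none or two of them with an event), following the full-period condition moves the estimate by about 3 points either way, well inside the interval around 14.8%. The analysis is single-arm and descriptive, and the supplied text attaches no test or decision threshold to it.

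Two further inferences go too far. A reader might conclude that the plan has no rule for these participants. It has a usable one in 4.3, and the Analysis Implementation Plan or the full protocol, neither supplied, may settle precedence. A reader might also conclude that the evaluation at the final recommended dose needs the same correction. That is a separate analysis, to be done only if possible, with its own stated inclusion rule, and 4.3 does not address it.

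**What to change.** 1. In SAP 4.1, the first sentence of 4.3 and the next protocol amendment or memorandum, define the primary set as all participants whose BDQ exposure, for as long as they were on study drug, was at their cohort's final implemented dose, whatever its duration, plus those dose-reduced for toxicity. Keep the exclusion of PK-adjusted participants and its sensitivity analysis.
2. In 4.1 and the protocol text, replace the unqualified failure statement with the 4.3 rule. Toxicity removals and dose reductions are failures for the relevant outcome only. Non-toxicity leavers are included and are failures only for outcomes that occurred on study drug.
3. Extend the two 4.3 sensitivity analyses (worst case and exclusion) to participants who stop BDQ before Week 24 for non-toxicity reasons but remain on study.

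Leave the evaluation at the final recommended dose as it is. The cost is wording in two SAP sections and one protocol text, plus a slightly larger sensitivity analysis. No new data are needed. The changes should be made before the primary analysis is run.
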